COMIRB Protocol

COLORADO MULTIPLE INSTITUTIONAL REVIEW BOARD
[name] [contact] [contact]

Protocol #: 16-1785

Project Title: Evaluation of Moderate to Severe Influenza Disease in Children 6 months to 8 years in Colorado

Principal Investigator: [name]

Version Date: 7/27/16

I. Hypotheses and Specific Aims:

Children 6 months to 8 years of age with moderate to severe influenza have a higher risk of hospitalization, intensive care unit (ICU) admission, antibiotic use and complications compared with children with mild influenza illness.

Specific Aims:

Aim #1: To determine the validity of the moderate to severe endpoint for influenza as a predictor for hospitalization among children aged 6 months to 8 years evaluated at Children's Hospital Colorado (CHCO) emergency department (ED) and urgent cares (UC) during the 2016-2017 influenza season.

Aim #2: To prospectively evaluate the usefulness of the moderate to severe influenza endpoint against additional severity measures such as ICU admission, antibiotic and antiviral use, parental and child absenteeism and recurrent healthcare visits among children aged 6 months to 8 years evaluated at ED and UC centers in Colorado.

Aim # 3: To compare the healthcare costs associated with management of moderate to severe versus mild influenza disease.

Exploratory Objectives:

- 1) To compare the moderate to severe influenza definition, and other severity measures such as ICU admission, hospitalization, antibiotic, antiviral use, child and caregiver absenteeism among patients vaccinated with injectable influenza vaccine (IIV) versus unvaccinated individuals.
- 2) To evaluate severity measures such as hospitalization, ICU admission, antibiotic, antiviral use, caregiver and child absenteeism among children with influenza like illness who test negative for influenza.
- 3) To determine whether clinical measurements taken at ED/UC presentation such as systemic inflammatory response syndrome (SIRS) criteria, adjusted heart rate, oxygen saturation and temperature predict hospitalization, ICU admission and having polymerase chain reaction (PCR)-confirmed influenza. We will also consider the prediction value of peak temperature and temperature duration.

II. Background and Significance:

Influenza is an important cause of morbidity in children, annually causing 1-7 hospitalizations per 10,000 in US children under the age of 18 years (1-6). Children are

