Preliminary data from the 2013-2014 and 2014-2015 influenza seasons demonstrated that among 11,997 patients who presented to CHCO ED, UC or outpatient clinics for an acute respiratory illness, 1398 (12%) underwent viral testing (either respiratory pathogen panel multiplex PCR or influenza PCR). 1375 patients were admitted for a respiratory illness, and of these, 994 (72%) underwent viral testing. Additional data regarding ED visits during these time periods are shown in Table 2.

Table 2. Children Presenting to CHCO ED or UC with Acute Respiratory Illness, 2013-2014 and 2014-2015

CHCO data:	2013-2014	2014-2015	Total
ED/UC/Clinic visits due to an acute respiratory illness	5900	6097	11997
ED visits due to an acute respiratory illness, limited to patients < 8 yrs	4510	4595	9105
ED visits limited to CHCO, Uptown Urgent Care, South Urgent Care with an acute respiratory illness, limited to patients < 8 yrs	2703	2809	5512
ED visits with above restrictions further limited to Jan to March	1290	1745	3035
Limit visits to < 8 yrs Jan to March, no repeat visits	1244	1688	2932
Admission for acute respiratory illness,	454	486	940

Jan -Mar

IV. Research Methods

The study comprises a prospective analysis of children presenting to CHCO ED, and North Campus UC with an influenza-like illness (ILI) during the 2016-2017 influenza season. Once enrolled in the study, we will collect respiratory samples (nasopharyngeal (NP) specimens), socio demographic, and clinical data including variables of interest outlined above, and follow the clinical outcome of these children for 14 days after their initial presentation. A complete list of the variables being collected can be found in Appendix A.

A. Outcome Measure(s):

Primary outcome measure /Endpoints:

- 1) Hospitalization in patients presenting to the CHCO Main ED or North Campus UC with influenza

Secondary outcome measures/Endpoints:

- 1) ICU admission in patients presenting to the CHCO Main ED or North Campus UC with influenza
- 2) Antiviral use in patients presenting to the CHCO Main ED or North Campus UC with influenza
- 3) Antibiotic use in patients presenting to the CHCO Main ED or North Campus UC with influenza
- 4) Number of visits to the ED or healthcare provider in patients presenting to the CHCO Main ED or North Campus UC with influenza
- 5) Number of days of absenteeism from school or daycare in patients presenting to the CHCO Main ED or North Campus UC with influenza

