- 6) Number of days of absenteeism from work in caregivers of children presenting to the CHCO Main ED or North Campus UC with influenza
- 7) Healthcare costs associated with ED visits or hospitalization in patients presenting to the CHCO Main ED or North Campus UC with influenza

Exploratory Outcome measures/Endpoints:

1) Vaccination status in subjects testing positive for influenza:

- a. Injectable influenza vaccine (IIV) receipt in patients presenting to the CHCO Main ED or North Campus UC with moderate to severe influenza
- b. IIV receipt in patients presenting to the CHCO Main ED or North Campus UC who are hospitalized
- c. IIV receipt in patients presenting to the CHCO Main ED or North Campus UC who are admitted to the ICU
- d. Number of days of fever in patients who received IIV presenting to the CHCO Main ED or North Campus UC
- e. Number of days of caregiver and child absenteeism in patients who received IIV presenting to the CHCO Main ED or North Campus UC

- f. IIV receipt in patients presenting to the CHCO Main ED or North Campus UC who received antibiotics
- g. IIV receipt in patients presenting to the CHCO Main ED or North Campus UC who received antivirals

2) Influenza-like-illness among subjects testing negative for influenza:

- a. Hospitalization in patients with ILI who test negative for influenza
- b. ICU admission in patients with ILI who test negative for influenza
- c. Duration of fever in patients with ILI who test negative for influenza
- d. Number of days of absenteeism from work in caregivers of patients with ILI who test negative for influenza
- e. Number of days of absenteeism from school in patients with ILI who test negative for influenza
- f. Antibiotic use in patients with ILI who test negative for influenza
- g. Antiviral use in patients with ILI who test negative for influenza

3) Fever, vital sign data and extrapulmonary complications:

- a. Number of days of fever in patients presenting to the CHCO Main ED or North Campus UC with influenza
- b. Peak temperature at any time during illness in patients presenting to the CHCO Main ED or North Campus UC with influenza
- c. Modified SIRS criteria met in patients presenting to the CHCO Main ED or North Campus UC with influenza
- d. Initial and peak adjusted heart rate in patients presenting to the CHCO Main ED or North Campus UC with influenza
- e. Oxygen saturation in patients presenting to the CHCO Main ED or North Campus UC with influenza

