- f. Extrapulmonary complications in patients presenting to the CHCO Main ED or North Campus UC with ILI

Definitions:

Influenza like illness (ILI): child with temperature of $\geq 37.8^{\circ}\text{C}$ and at least one of the following: cough, sore throat, runny nose or nasal congestion

Influenza: child with respiratory test that is positive for influenza by PCR

Moderate to severe influenza: child with influenza and one or more of the following criteria:

1. fever $> 39^{\circ}\text{C}$,
2. presence of otitis media defined by AAP guideline criteria,
3. lower respiratory tract infection (shortness of breath, pulmonary congestion, pneumonia, bronchiolitis, bronchitis, wheezing, croup), or
4. serious extrapulmonary manifestations (e.g., myocarditis, encephalitis, seizure)(15).

Mild influenza: child with ILI symptoms, but do not have any of the criteria for moderate to severe influenza

SIRS: Defined as the presence of two or more of the following, one of which must be abnormal temperature or leukocyte count:

1. core temperature <36 or >38.5°C
2. tachycardia (or bradycardia in infants),
3. tachypnea

Modified SIRS criteria (18): same definition as SIRS criteria excluding neutrophil criteria, i.e. the presence of two or more of the following, one of which must be abnormal temperature :

1. core temperature <36 or >38.5°C
2. tachycardia (or bradycardia in infants),
3. tachypnea

Tachycardia and tachypnea definitions by age:

Age group	Tachycardia	Bradycardia	Respiratory rate
1 month-1 year	>180	<90	>34
2-5 years	>140	NA	>22
6-12 years	>130	NA	>18

B. Description of Population to be Enrolled:

Population:

Children 6 months to 8 years of age seeking evaluation and management of ILI at the Main CHCO ED or North Campus UC will be eligible for participation in the study. The study will commence during the influenza season as determined by the department of microbiology and epidemiology at CHCO (the influenza season commences when there are 3 positive influenza PCR tests within a week). The study will continue for 5 months following the start of the influenza season.

Inclusion criteria:

- 1) Age 6 months \leq 8 years
- 2) Presentation to the CHCO Main ED or North Campus UC with signs and symptoms of ILI (temperature of $\geq 37.8^{\circ}\text{C}$ and at least one of the following: cough, sore throat, runny nose or nasal congestion)
- 3) Patients seen during the 2016-2017 influenza season

Exclusion criteria:

- 1) Respiratory symptom duration $>$ 14 days

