Aim #3/Secondary Endpoint #7 Analysis: An economic analysis will be conducted to compare the healthcare costs in the mild and moderate to severe influenza groups. We will work with the finance department at CHCO to obtain charge data for each influenza-related ED visit and hospitalization. Direct costs associated with healthcare utilization will be obtained by collecting hospital charge data and applying a cost to charge ratio to estimate costs. Mean costs and standard deviations for each group will be determined and compared using t tests for normally distributed data, and presented as median (IQR) costs with analysis conducted using non parametric tests for non-normally distributed data. Relative healthcare costs will be modeled on log-transformed data using linear regression or a generalized linear model, depending on the data distribution.

Exploratory Objective #1-2/Exploratory Endpoints #1-2: In addition to the primary and secondary outcomes outlined above, we will also assess the odds ratios and 95% CI of several exploratory dichotomous outcomes –moderate to severe influenza, hospitalization, ICU admission, antibiotics and antiviral use among patients with IIV versus unvaccinated children using log linear regression in a manner similar to the above specific aims. For continuous variables (duration of fever, number of days of absenteeism), we will use a log linear model as described for our prior secondary outcomes.
We will conduct a similar analysis as outlined above for patients with influenza like illness who test negative for influenza using the clinical severity outcome measures outlined.

Exploratory Objective #3/Exploratory Endpoint#3: We will determine the predictive value for hospitalization, ICU admission and having PCR-confirmed influenza of duration of fever, SIRS criteria, adjusted heart rate, respiratory rate and oxygen saturation using logistic regression models with two-way interactions between factors in the model when needed. We will use the Brier score to assess overall model performance and the c statistic to assess discriminative ability. In addition to logistic regression, we will explore machine learning methods for the predictive modeling of these three outcomes. The predictive value of peak temperature will also be assessed using a logistic regression model.

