To compare temperature trajectories between hospitalized and non-hospitalized, we will use a linear mixed model. This will allow us to use all of the longitudinal temperature measurements to measure the mean temperature trajectory of patients in one group (e.g. hospitalized patients) compared to the other (e.g. non-hospitalized patients). We will accomplish this by including an interaction term between time and hospitalization status, which will give us hospitalization status-specific trajectories. We will do this for each

dichotomous outcome: hospitalization, ICU status, influenza diagnosis. This method is preferred over subgroup analysis because it will optimize statistical power.

[figure not shown]
Two sensitivity analyses will be conducted. Firstly, analyses will be restricted to patients presenting to the main CHCO ED. Secondly, to further evaluate whether temperature $> 39^{\circ}\text{C}$ is a predictor of healthcare utilization or poorer outcomes, an analysis of each of the secondary outcome measures will be conducted. Firstly, we will compare all moderate to severe versus mild influenza cases. If these reach statistical significance with an odds ratio > 1 , we will then repeat the analysis with a definition of moderate to severe influenza as solely temperature $> 39^{\circ}\text{C}$.

Power and sample size calculations:

Using historical data from our institution, a sample size of 408 patients (of which we assume 30% have mild flu and 70% have moderate/severe flu) will achieve 80% power at a 0.05 significance level to detect an odds ratio of approximately 2 for hospitalization among the moderate/severe compared to the mild cases, accounting for the inclusion of correlated covariables in our multivariable model. Assuming that 25% of patients tested will be influenza positive (19) during the influenza season; we will need to test approximately 1632 subjects (Figure 1). A sample size of 151 patients with the same assumptions, power and significance level will detect an odds ratio of 3 for hospitalization among the moderate/severe compared with mild cases, so 604 subjects will need to be tested.

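### The cost endpoint names only ED visits and hospitalizations although children are also enrolled at urgent care, so the cost of an urgent-care-only child is undefined

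*Combined protocol and SAP*

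**What the plan says.** Aim #3 in Section I sets no limit by care setting: "To compare the healthcare costs associated with management of moderate to severe versus mild influenza disease".

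Inclusion criterion 2 in Section IV.B makes urgent care an enrolment site: "Presentation to the CHCO Main ED or North Campus UC with signs and symptoms of ILI".

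Secondary endpoint 7 in Section IV.A reads "Healthcare costs associated with ED visits or hospitalization in patients presenting to the CHCO Main ED or North Campus UC with influenza". Both sites define the population, but only the ED and the ward define the costed events.

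The Aim #3 paragraph of Section IV.F repeats this. The team will "obtain charge data for each influenza-related ED visit and hospitalization", and direct costs come from "collecting hospital charge data and applying a cost to charge ratio to estimate costs". Groups are compared with t tests, or with medians and non-parametric tests, and then "Relative healthcare costs will be modeled on log-transformed data using linear regression or a generalized linear model", depending on the distribution. The paragraph has no rule for a child with zero or no cost.

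**The concern.** A child who came to North Campus UC, was sent home and had no later ED visit or admission has no costed event if the text is applied as written. The visit that made the child eligible is then missing from that child's cost. Such a child must be left out, set to zero or handled by a rule that the plan does not give.

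The Aim 3 result compares costs between severity groups. If the two groups used urgent care to different extents, the gap falls unequally on them and the ratio can change for reasons unrelated to the cost of the disease. Someone in finance who receives the Aim 3 text could reasonably extract ED and inpatient charges only.

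**Working it through.** **Text.** Endpoint 7 and the Aim #3 analysis agree with each other, so the omission is not a slip in one place. Neither names UC visits, and neither expressly excludes them. Usage of the term elsewhere is mixed:

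- Written jointly for ED and UC: exploratory objective 3 (Section I), the discharge memory aid (IV.C, Surveillance Methods) and specimen collection (IV.D).
- ED used to include urgent care: a Table 2 row in Section III, "ED visits limited to CHCO, Uptown Urgent Care, South Urgent Care with an acute respiratory illness", and Section IV.E, which describes selection for the whole study as patients presenting to the ED.

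The words alone therefore do not settle whether the UC index visit is costed.

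**Arithmetic.** The plan gives no cost figure, cost ratio or UC share, so there is nothing to reproduce. The following only illustrates whether the choice can matter.

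*From the plan:* an odds ratio of about 2 for hospitalization (power section of IV.F).

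*Assumed, not in the documents:* ED visit cost 1, UC visit 0.4, hospital stay 5 (relative units); 10% of mild children hospitalized; the same hospitalization share at both sites; no later ED or UC visits. Mild odds are 0.10/0.90 = 0.111; doubled, 0.222; so the moderate-to-severe share is 0.222/1.222 = 0.182.

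With u the share enrolled at UC and h the share hospitalized, the mean cost per group is:

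- UC visit costed: (1 − u) + 0.4u + 5h
- UC visit set to zero: (1 − u) + 5h
- UC-only children dropped: [(1 − u) + 5h] / [1 − u(1 − h)]

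Take UC shares of 60% in mild and 30% in moderate-to-severe children:

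- Costed: mild 0.40 + 0.24 + 0.50 = 1.14; moderate-to-severe 0.70 + 0.12 + 0.909 = 1.729; ratio 1.52.
- Zero: 0.90 and 1.609; ratio 1.79.
- Dropped: the shares without cost are 0.60 × 0.90 = 0.54 and 0.30 × 0.818 = 0.245. The means are 0.90/0.46 = 1.957 and 1.609/0.755 = 2.13; ratio 1.09.

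The geometric mean ratio, which a linear model on log cost estimates, comes from averaging log cost over the same four site-by-hospitalization cells.

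| UC share, mild / mod-severe | Mean ratio, UC costed | UC set to zero | UC-only dropped | Geometric ratio, UC costed | Geometric, UC-only dropped |
|---|---|---|---|---|---|
| 60% / 30% | 1.52 | 1.79 | 1.09 | 1.52 | 1.05 |
| 25% / 25% | 1.30 | 1.33 | 1.29 | 1.18 | 1.19 |
| 30% / 50% | 1.22 | 1.17 | 1.45 | 1.01 | 1.33 |

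Further scenarios used other UC shares (25-60% of mild, 25-50% of moderate-to-severe children), a UC visit at 0.4-0.8, a stay at 5-10 and mild hospitalization of 10-20%. Across these and the rows above, the mean ratio is 1.22-1.61 with UC costed, 1.17-1.80 with UC at zero, and 1.09-1.68 with UC-only children dropped.

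**The case against.** The strongest reply is that an ED visit in the cost text may already include a UC visit. Table 2 and Section IV.E use the term that way, Aim #1 describes the urgent cares as belonging to the same hospital, and that hospital's finance department supplies the charges. This stands as far as it goes: the term is ambiguous. A reader might infer that the protocol always names both sites when it means both, and so that UC charges are excluded. The documents do not support that. But nothing in them brings UC charges into the main cost analysis either.

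Second, the undefined logarithm is only one route. Medians, rank tests and some generalized linear models accept zeros. That is correct, but a zero accepted by the method is still a visit left uncosted. The literal gap also covers only UC children without a later ED visit or admission, so it is smaller than the whole UC group.

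Third, a planned sensitivity analysis says that "analyses will be restricted to patients presenting to the main CHCO ED". Every child in it has an index ED visit. Applied to costs, it would expose the problem, but it removes UC children rather than costing them and so does not repair the main analysis.

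Finally, costs of ED and inpatient care alone could be a deliberate choice. That would be a narrower quantity than Aim 3 describes, and the plan should say so.

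**Conclusion.** The point holds as a gap in the definition of a secondary endpoint; the primary analysis is not affected. As written, the costed events leave out the index visit of a child seen only at UC, and the plan does not say how that child enters the analysis.

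A reader might go further and infer that the cost ratio is biased, and in a known direction because UC children are milder. The documents do not support this. They give neither the UC share by severity nor any unit cost, and in the illustration the ratio moves up, down or hardly at all, depending on the site mix and on whether UC-only children are set to zero or dropped. All figures in the table rest on the stated assumptions and are not estimates for this study. What can be said is that the ratio may be distorted in either direction, and that an unstated handling choice could change it materially.

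**What to change.** Change the costed events in endpoint 7 and in the Aim #3 paragraph of Section IV.F to: *each influenza-related ED visit, UC visit (including the index visit) and hospitalization through the 14-day follow-up*. Request UC charges in the same finance extract. If UC costs are left out on purpose, say so and state how children with no costed event are analysed.

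The cost is two wording changes and one more charge category in a request that is already planned. No extra contact with families is needed.

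### Exploratory Objective #3 uses whole-illness peak temperature to predict admission, leaves the window for fever duration and heart rate open, and states no internal validation for its prediction models (low severity)

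*Combined protocol and SAP*

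**What the plan says.** Section I, Exploratory Objective 3, asks whether "clinical measurements taken at ED/UC presentation", with SIRS, adjusted heart rate, oxygen saturation and temperature as examples, predict hospitalization, ICU admission and PCR-confirmed influenza. A second sentence goes beyond presentation: "We will also consider the prediction value of peak temperature and temperature duration".

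Section IV.A, exploratory endpoint group 3, defines the variables. Item 3a is "Number of days of fever in patients presenting to the CHCO Main ED or North Campus UC with influenza", with no end point for the count. Item 3b is "Peak temperature at any time during illness". Item 3d lists both an initial and a peak adjusted heart rate.

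Section IV.F, Exploratory Objective #3, gives the analysis: "We will determine the predictive value for hospitalization, ICU admission and having PCR-confirmed influenza of duration of fever, SIRS criteria, adjusted heart rate", together with respiratory rate and oxygen saturation. The models are logistic, with "two-way interactions between factors in the model when needed". On performance: "We will use the Brier score to assess overall model performance and the c statistic to assess discriminative ability". Machine learning is to be explored for the same three outcomes. Then: "The predictive value of peak temperature will also be assessed using a logistic regression model".

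Children are followed for 14 days after presentation (Section IV, opening paragraph). Section IV.F also plans a mixed model on serial temperatures by hospitalization status. In the readable part of Appendix A, fever duration stands under the follow-up heading.

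**The concern.** A predictor of admission has to be known when admission is decided. A maximum taken over the whole illness is not. An admitted child is likely to have more recorded temperatures than a child sent home, and a maximum over more readings is higher on average even if the two children are equally febrile. Part of the apparent predictive value could then be a result of being admitted. Total fever days raise the same problem if they include days after admission, and so does peak heart rate.

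The validation gap is a separate matter. A c statistic or Brier score computed on the children used to fit the model is optimistic. The optimism grows as events become fewer and terms more numerous, and it is a particular risk for interactions chosen from the data and for tuned machine learning models. ICU admission is the outcome most exposed.

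At stake is how the exploratory results are read: a reported c could be taken as what the vital signs and temperature could tell a clinician at the visit.

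**Working it through.** **1. Time window, variable by variable**

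| Predictor | Objective (Section I) | Endpoint (Section IV.A) | Model (Section IV.F) | Status |
|---|---|---|---|---|
| Peak temperature | no limit | whole illness | no limit | post-admission readings included as written |
| Fever duration | no limit | no cut-off | no limit | open; follow-up item in readable Appendix A |
| Adjusted heart rate | presentation | initial and peak | not specified | open |
| SIRS, oxygen saturation | presentation | no later value named | not specified | not in question |

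The plan gives no figure to reproduce here. The simulations below show direction and rough size only.

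**2. Peak temperature with no true link to admission** (assumed: 200,000 children, normal readings, score = maximum reading)

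| Later readings, admitted / others | c, within-child correlation 0.3, 2 early readings | c, correlation 0.85, 3 early readings |
|---|---|---|
| 4 / 2 | 0.573 | 0.520 |
| 6 / 2 | 0.620 | 0.536 |
| 12 / 2 | 0.702 | 0.564 |
| 4 / 4 | 0.501 | 0.499 |

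With early readings only, c is 0.498 to 0.502. The excess comes entirely from unequal counts of later readings.

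The cut-off must also be the same for all children. If it is the admission decision, 10 to 30% of admissions come late, and only those children gain 2 to 4 extra readings, the null c is 0.505 to 0.559. With an index-visit cut-off for every child it is 0.500 to 0.502.

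**3. Fever duration, if total days were used.** Assumed: four other predictors with log odds ratio 0.25 each; pre-visit fever days unrelated to the outcome; outcome rates of 4%, 11% and 32%; later fever d days longer on average in children with the outcome.
- Pre-visit days only: c = 0.667 to 0.674.
- Total days, d = 0: 0.667 to 0.674 (no effect).
- d = 0.5: 0.674 to 0.691. d = 1: 0.690 to 0.727. d = 2: 0.727 to 0.812.

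Table 1 gives median fever of 2 and 4 days in the two age groups of admitted children, but not how much followed admission. So d is unknown and zero is possible.

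**4. Optimism in c.** Events are assumed from the protocol's historical figures:
- Hospitalization: 1375/11,997 = 11.5% (Section III) to 940/2932 = 32% (Table 2). 408 × 0.1146 = 47; 408 × 0.3206 = 131.
- ICU among hospitalized (Table 1): (55 + 81)/395 = 0.344. 46.8 × 0.344 = 16; 130.8 × 0.344 = 45.
- With all 1632 tested children, every count is four times as large: 187 to 523 and 64 to 180.

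Simulation: five normal predictors with correlation 0.2 and log odds ratio 0.25 each, 1000 replicates. Optimism = apparent c minus c in 12,000 new children. Fifteen terms means 5 main effects plus all 5 × 4/2 = 10 two-way interactions.

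| Outcome | N | Events | 5 terms | 15 terms |
|---|---|---|---|---|
| ICU | 408 | 16 | 0.081 | 0.176 |
| ICU | 408 | 45 | 0.037 | 0.094 |
| Hospitalization | 408 | 47 | 0.035 | 0.092 |
| Hospitalization | 408 | 131 | 0.017 | 0.052 |
| ICU | 1632 | 64 | 0.021 | 0.059 |
| ICU | 1632 | 180 | 0.009 | 0.025 |
| Hospitalization | 1632 | 187 | 0.0085 | 0.024 |
| Hospitalization | 1632 | 523 | 0.004 | 0.013 |
| PCR influenza | 1632 | 408 | 0.0055 | 0.0147 |

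Brier optimism is about 0.016 at most. Machine learning was not simulated.

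**The case against.** **The whole-illness question may be deliberate.** The study validates an endpoint for vaccine trials, not a bedside rule, and Section I names peak temperature and duration apart from the presentation measurements. This stands as an account of intent. It supports reporting whole-illness values as associations, but it does not make a post-admission reading a predictor of admission.

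**Fever duration is only ambiguous.** Most of Appendix A is missing from the readable text, so a value recorded at presentation may exist. This stands. A reader might infer that follow-up fever days will certainly enter the model; the documents do not show that. Only peak temperature is expressly defined over the whole illness.

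**Peak temperature has no c statistic expressly attached.** Its model is described after the performance measures. This stands; c in step 2 is a yardstick for the bias, not a stated output.

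**The sizes rest on assumptions.** This stands. Reading counts and fever differences have no source in the protocol. The 940 and 2932 in Table 2 appear to carry different restrictions. The 11.5% includes clinic visits. The 34% comes from influenza inpatients, and its use for all 1632 tested children is weaker still. Interactions enter only when needed, so 15 terms is an extreme case. With five terms and all 1632 children, optimism is small.

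**No decision hangs on an exploratory c.** Largely true, and the reason for the low rating.

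**Conclusion.** Two gaps hold. First, following the plan as written, post-admission readings can enter the peak-temperature model for hospitalization and ICU admission. For fever duration and adjusted heart rate the plan does not settle which value is used. Second, models with data-dependent interactions and machine learning models are to be judged by c and Brier with no internal validation stated in any readable section.

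The direction is firm if admitted children have more readings: apparent predictive value is too favourable. The size is not. Under the assumptions shown, a peak temperature with no predictive value reaches c of 0.52 to 0.70. Optimism with five terms and 408 children is 0.04 to 0.08 for ICU admission and 0.02 to 0.04 for hospitalization. With equal reading counts the first effect vanishes; with many events the second is small.

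A reader might go further and infer that all Objective 3 predictors are contaminated, or that Aim 1 shares the defect or is free of it. The first is not supported: SIRS and oxygen saturation are tied to presentation. On Aim 1 nothing is concluded here; the time window in the moderate-to-severe definition is a separate question. Nor does the leakage argument extend to PCR-confirmed influenza, which is not a decision that later temperatures follow.

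Severity is low, because the objective is exploratory.

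**What to change.** In Section IV.F, Exploratory Objective #3:

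1. For the hospitalization and ICU models, use only values recorded up to a cut-off that is the same for every child and does not depend on the outcome. One option is the end of the index ED/UC visit, with later admissions still counted as events. Name the variables: initial adjusted heart rate, peak temperature to that point, and fever days to that point if they are recorded.
2. Report whole-illness peak temperature, peak heart rate and total fever duration as descriptive associations with admission, not as predictive value.
3. For every logistic and machine learning model, report bootstrap optimism-corrected or cross-validated c and Brier, with interaction selection and tuning repeated inside each resample.

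As a side clarification, state whether the hospitalization and ICU models use influenza-positive children or all tested children, since the event count depends on it.

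The cost is a few sentences and some analysis time. Reported performance may look less favourable. If fever days up to the visit were not recorded, fever duration can be described but not used to predict admission.
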